3.3.6 Washout Period

- 4-weeks for any topical or systemic corticosteroids, anti-inflammatories, antibiotics,
- 3-months for any systemic retinoids or biologics, or any investigational treatment
- Only specific procedures are performed as indicated in the table of Schedules of

Events, if subjects need washout periods

3.4 Treatment Plan

3.4.1 Administration

3.4.1.1 Treatment group:

TC Cream: 0.3g/cm², applied to the afflicted area after cleaning the skin with warm water; twice daily (morning and evening); dosage should not exceed 25g/day.

3.4.1.2 Control group (placebo):

Vehicle of TC Cream: 0.3g/cm², applied to the afflicted area after cleaning the skin with warm water; twice daily (morning and evening); dosage should not exceed 25g/day.

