Study Design	Multi-center, randomized, double blind (Subject, Investigator), placebo controlled, parallel assignment
Study Agent /Intervention Description	
Treatment group: TC Cream: 0.3g/cm², applied to afflicted area after cleaning the skin with warm water; twice daily (morning and evening); dosage should not exceed 25g/day
 
Control group (placebo): Vehicle of TC Cream: 0.3g/cm², applied to afflicted area after cleaning the skin with warm water; twice daily (morning and evening); dosage should not exceed 25g/day

Concomitant Medications/ Therapies	None
Safety Considerations and Monitoring of adverse events	Do not expect any side effect other than mild red pigmentation which will disappear after the drug withdrawal.
Diagnosis and Main Inclusion Criteria	
 ✓ Male or female of 18-70 years old ✓ Women of childbearing age must be using birth control strategies defined by one of the following: 1) a barrier method (condom) and 2) oral contraceptives, during the 8-weeks study period. ✓ Consistent with diagnostic criteria of psoriasis vulgaris ✓ ISGA score ≥ 2 (at least mild severity) ✓ BSA (stable stage group): $1\% \leq$ to $\leq 20\%$ 
Note: Randomized, male-female ratio should be properly taken into consideration.

Main Exclusion Criteria	
 ✓ Subjects in pregnancy, preparing for pregnancy or breast feeding ✓ History of hyperergic or photosensitivity ✓ History of complicated cardiovascular disease, cerebrovascular disease, severe primary diseases in hepatic, kidney and hematopoietic system, or patients who are diagnosed with psychotic disorders ✓ Within 2/4 weeks prior to randomization the patients have taken treatment with following approved or investigational psoriasis therapy of the target lesions: 
 ○ Topical treatments ○ PUVA, UVB or Grenz ray therapy ○ Any systemic treatments other than biologicals with a possible effect on psoriasis (e.g., corticosteroids, vitamin D analogues, retinoids, hydroxycarbamide, azathioprine, methotrexate, cyclosporine, other immunosuppressants).

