1.4 Route of Administration

The study agents are for external/topical use only. Apply a thin layer (0.3g/cm²) of TC Cream to the affected area(s) twice daily. Daily doses exceeding 50g have not been systematically studied.

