3. STUDY DESIGNS

This is a double-blind, randomized, placebo-controlled, parallel-controlled, multi-center, phase II^b clinical trial.

This phase II^b clinical trial includes two study groups: a treatment group and a placebo

Protocol Version: 00

group, and it will be conducted at multiple centers. The total number of sample cases needed for this trial is 88 patients enrolled. The subjects are both inpatients and outpatients with BSA $\geq 1\%$ to $\leq 20\%$. Approximate time to complete study enrollment is 1~2 days. The expected duration of subject participation is 8 weeks. After the initial 8 weeks of treatment, there will be a 4-week follow-up period during which no treatment is used.

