3.3.4 Inclusion Criteria

- Age of 18-70 years old. Both men and women, and members of all races and ethnic groups, will be included
- Consistent with the diagnostic criteria of stable-stage psoriasis vulgaris, and have at least two target lesions suitable for evaluation

Protocol Version: 00

- Women of childbearing age must be using birth control strategies defined by one of the following: 1) a barrier method (condom) and 2) oral contraceptives, during the 8-week study period.
- ISGA score ≥ 2 (at least mild severity)
- BSA (stable stage group): $1\% \leq$ to $\leq 20\%$
- Signed a written informed consent document
- No additional exposure to the sun

Note: Randomized, male-female ratio should be adequately taken into consideration.

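### The stated rate of 0.3 g/cm² twice daily cannot be applied to all affected skin within the 25 g/day cap for any eligible adult at entry

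*Combined protocol and SAP*

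**What the plan says.** The rate appears in three places. Section 3.4.1 gives it for the active arm, "TC Cream: 0.3g/cm², applied to the afflicted area", and for the control arm, "Vehicle of TC Cream: 0.3g/cm², applied to the afflicted area". The Protocol Synopsis (Study Agent/Intervention Description) repeats it for both arms. Section 1.4 gives it once more: "Apply a thin layer (0.3g/cm²) of TC Cream to the affected area(s) twice daily".

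In section 3.4.1 and the synopsis the rate stands in one instruction with the frequency and the daily limit: "applied to the afflicted area after cleaning the skin with warm water; twice daily (morning and evening); dosage should not exceed 25g/day". Section 1.4 does not repeat the limit, but adds: "Daily doses exceeding 50g have not been systematically studied".

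The area to be treated is bounded by eligibility. The synopsis, section 3 and section 3.3.4 all admit patients with 1% to 20% of body surface affected, and section 3.3.4 limits entry to ages 18-70. The available text does not restrict treatment to part of the lesions. It also does not say how to proceed when area times rate exceeds the limit.

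**The concern.** A daily maximum next to a per-area rate normally limits the extremes: most patients use the rate, and those with extensive disease meet the ceiling. Here the ceiling lies below what the rate requires even at the smallest eligible area, so at entry the two parts of the instruction cannot both be met over the whole affected skin of any patient.

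What is at stake is the dose description. This is a Phase IIb trial, and its report has to say what was applied. A report that repeats 0.3 g/cm² twice daily to the affected area would describe a regimen that nobody could have followed within the cap at entry. Patients and site staff also receive an instruction with two parts that conflict, and each must work out alone how to reconcile them.

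**Working it through.** **Inputs from the documents.** Rate 0.3 g/cm², two applications a day, cap 25 g/day (section 3.4.1 and synopsis); affected area 1-20% BSA (synopsis, sections 3 and 3.3.4); adults only (section 3.3.4).

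**Assumption.** Adult total body surface is not in the documents. I take 1.5-2.2 m², with a wider check at 1.3-2.5 m².

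**Two readings of the rate.** Per application, the daily need is 0.3 × 2 = 0.6 g per cm². As a daily total, it is 0.3 g per cm². The cap is a stated limit and not the result of a calculation, so there is no plan figure to reproduce.

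**Step 1: area that the cap covers.** Area = 25 / daily need per cm².
- Per application: 25 / 0.6 = 41.7 cm².
- Daily total: 25 / 0.3 = 83.3 cm².

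**Step 2: body surface at which 1% BSA just fits the cap.** Total surface = area / 0.01.
- Per application: 41.7 / 0.01 = 4,170 cm² = 0.42 m².
- Daily total: 83.3 / 0.01 = 8,330 cm² = 0.83 m².

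The conflict therefore holds for anyone with a total surface above 0.83 m² on either reading. The exact adult value affects only its size.

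**Step 3: daily need and share of the stated rate.** 1% BSA is 150-220 cm²; 20% BSA is 3,000-4,400 cm². Share = 25 / need, which is the average over all affected skin when the full 25 g is spread evenly.

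| Reading | BSA | Need (g/day) | Multiple of cap | Share of stated rate at the cap |
|---|---|---|---|---|
| Per application | 1% | 150 × 0.6 = 90 to 220 × 0.6 = 132 | 3.6 to 5.3 | 27.8% to 18.9% |
| Per application | 20% | 1,800 to 2,640 | 72 to 106 | 1.4% to 0.9% |
| Daily total | 1% | 150 × 0.3 = 45 to 220 × 0.3 = 66 | 1.8 to 2.6 | 55.6% to 37.9% |
| Daily total | 20% | 900 to 1,320 | 36 to 53 | 2.8% to 1.9% |

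**Step 4: wider range.** At 1.3-2.5 m², 1% BSA is 130-250 cm² and needs 78-150 g/day per application, or 39-75 g/day as a daily total. Both ranges lie wholly above 25 g/day.

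**Step 5: dose at the cap for one example.** With 1.7 m² and 12.5 g per application, the average is 12.5 / 170 = 0.074 g/cm² at 1% BSA and 12.5 / 3,400 = 0.0037 g/cm² at 20% BSA. If the cap is used in full, disease extent sets the dose per area, over a 20-fold range.

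**The case against.** The strongest reply is that the plan already resolves the conflict. The limit is worded as something not to be exceeded and sits in the same instruction as the rate, so an ordinary reader lets it govern. That stands. What it leaves open is how 25 g is distributed: as a thinner layer everywhere, over part of the lesions, or in fewer applications.

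A reader might infer more than the documents support:

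- **That the stated rate is never delivered.** A patient could apply the full rate to part of the lesions, up to 41.7 cm² (83.3 cm²). A responder whose lesions shrink below that area could later apply it everywhere. What is shown concerns all affected skin at entry, and the percentages are averages over that area.
- **That the dose is undefined.** A nominal rate, a thin layer and a daily maximum are all stated. The fault is that they do not fit together.
- **That patients are sent above 50 g/day.** On the per-application reading the uncapped need at 1% BSA exceeds 50 g/day above 0.83 m² (50 / 0.6 = 83.3 cm²). On the daily-total reading it does so above 1.67 m² (50 / 0.3 = 166.7 cm²). Either way the cap must be ignored first; a patient who obeys it stays below 50 g/day.
- **That the comparison is biased.** Both arms carry the same instruction, and no endpoint or analysis uses grams per cm².
- **That the figure is a decimal or unit slip.** Describing 0.3 g/cm² as thin invites this, since at an assumed density of 1 g/cm³ the layer would be 3 mm deep. The documents do not confirm it, and the same figure is repeated in the synopsis, section 1.4 and both arms of section 3.4.1.

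It is also fair to note that the schedule of events, kit labels and consent pages are not in the available text, so another per-area instruction could stand there.

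**Conclusion.** The point holds as an incompatibility in the dosing text. At entry, no eligible adult can apply 0.3 g/cm² twice daily to all affected skin within 25 g/day. The need at 1% BSA is 3.6-5.3 times the cap, or 1.8-2.6 times if the rate is a daily total, and at 20% BSA it is 20 times larger again. The existence of the conflict rests only on adults having more than 0.83 m² of total surface; its size rests on the assumed 1.5-2.2 m².

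The consequence is limited to the dose description and to instructions that can be followed. Sample size, randomisation, endpoints and the comparison of TC Cream with vehicle are not affected. It should be fixed, because the figure is operative text and the correction is small.

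**What to change.** In the synopsis, section 1.4 and section 3.4.1 (both arms), delete 0.3 g/cm², or replace it with an amount per application that the sponsor confirms from its formulation data. No replacement value is proposed here, because the documents do not give one. In each place, state that all lesions are to be covered thinly twice daily, that total use must not exceed 25 g/day, and that where the area is large a thinner layer is spread over all lesions rather than leaving some untreated.

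Optionally, weigh the tubes that section 3.4.3 already has patients return at each visit, so that the report can give grams used per day by arm.

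The cost is a short amendment, which under section 10.5 needs the principal investigator's signature and IRB approval, and revised subject instructions. If the figure is deleted and not replaced, the trial has no per-area target; that is the price of the simpler option.

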3.4.2 Duration of Therapy

Subjects should continuously apply the study agent twice daily (morning and evening) for 8 weeks. 4 weeks after treatment is completed, patients are required to return for study follow-up.

3.4.3 Treatment Compliance

The participants will be instructed to return all unused or part-used medication and packaging from used medication at each visit. The Investigator may withdraw participants if they consider compliance unsatisfactory.

3.4.4 Concomitant Drug Treatment

The subjects can use emollients (non-medicated moisturizers) during the study, but not on the day of the visit.

Subjects enrolled in this study will not be taking concomitant medications for other diseases.

If drug therapy for other diseases is required during the study, the investigator/study director will decide whether to continue or discontinue the subject's participation, and any corresponding medications should be recorded.

3.4.5 Early Withdrawal of Subjects

In the absence of treatment delays due to adverse events, treatment may continue until one of the following criteria applies:

- Voluntary patient withdrawal
- The investigator's decision that it is in the patient's best interest to withdraw
- If the patient becomes pregnant

Protocol Version: 00

- Noncompliance
- Significant protocol violation
- Safety reasons if any of the following occur:
 - Disease progression
 - Intercurrent illness that prevents further administration of treatment
 - Unacceptable adverse events(s)
 - Patient decides to withdraw from the study, or
 - General or specific changes in the patient's condition render the patient unacceptable for further treatment in the investigator's judgment.
- For any reason, at the Sponsor's or Investigators' discretion

3.5 Agent Formulation and Procurement

3.5.1 Agents Accountability

The Investigator, or a responsible party designated by the Investigator, must maintain a careful record of the inventory and disposition of the study agent.

At the completion of the study, all unused study drug(s) will be returned to the sponsor unless authorized by the sponsor for appropriate disposal.

3.5.2 Study Agents Supply

The sponsor (PRIG) will supply sufficient quantities of the study drugs to allow completion of this study. Study agents (test and control) are supplied in identical 25g collapsible tubes.

Designated clinical staff will be responsible for monitoring the receipt, storage, dispensing, and accounting for all study medications in accordance with Good Clinical Practice (GCP) and FDA regulations.

The appearance and packaging of the placebo will be consistent with those of the investigational product. The subjects and the investigators couldn't distinguish them. The product name, strength, the manufacturer's name, and lot/batch number will be identified on each container. The control agent will also include an expiry date. The study drugs will be placed under appropriate storage conditions in an area with controlled access.

Every subject will receive a packaging kit; exterior and interior packages should be kept with their respective labels.

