1.3 Control Agent: Placebo

Vehicle of TC Cream with the same manufacturing formulation and process, without the drug substance added.

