3.2 Blinding

Double blinding: the subject(s), investigator(s), monitor, and, in some cases, data analyst(s) will be blinded from the treatment agents throughout the study.

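### The label rules in section 3.5.2 contradict its own statement that the two products cannot be told apart, and followed literally they could reveal the arm in a trial with an investigator-scored primary endpoint

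*Combined protocol and SAP*

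**What the plan says.** Section 3.5.2 (Study Agents Supply) makes three statements that support the blind. On the container: "Study agents (test and control) are supplied in identical 25g collapsible tubes". On the presentation: "The appearance and packaging of the placebo will be consistent with those of the investigational product". On the result: "The subjects and the investigators couldn't distinguish them".

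The same paragraph then sets the label content: "The product name, strength, the manufacturer's name, and lot/batch number will be identified on each container". The next sentence is "The control agent will also include an expiry date". No sentence says whether the TC Cream label carries an expiry date. On what happens to the labels, the section adds: "Every subject will receive a packaging kit; exterior and interior packages should be kept with their respective labels".

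Section 1.3 defines the control: "Vehicle of TC Cream with the same manufacturing formulation and process, without the drug substance added".

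Section 3.2 (Blinding) names the subject, the investigator and the monitor as blinded. For analysts it says only that "in some cases, data analyst(s) will be blinded from the treatment agents throughout the study". It does not say which cases.

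**The concern.** A blind that depends on matching tubes is only as good as the labels on them. If the label carries a true product name or strength, or a field that appears in one arm only, the tube itself discloses the allocation.

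This matters because the efficacy measures are judgements. ISGA, listed first among the primary endpoints in section 5.1, is the investigator's own grading. Target lesions (section 5.1.2) are graded on visible signs, although the section names no assessor. PASI is described as performed by a physician (section 5.1.3), and the PDI is filled in by the patient (section 5.1.4). Scores given by someone who knows the arm cannot be corrected in the analysis.

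**Working it through.** This is a check of the text against itself. No figure in the plan depends on it, so there is none to reproduce.

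**Step 1: can the statements in section 3.5.2 all hold?**

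| Item | What 3.5.2 says | Compatible with indistinguishable products? |
|---|---|---|
| Tube | Identical in both arms | Yes, but this describes the tube, not its label |
| Product name and strength | On each container | Only if both arms carry the same text, which is not stated. The control has no drug substance (1.3), so a truthful name or strength would differ by arm |
| Lot/batch number | On each container | Only if the number cannot be linked to an arm. If lots differ by arm, one unblinded subject could reveal others with the same lot |
| Expiry date | Stated for the control agent, nothing stated for TC Cream | Not if the date is an extra item on the control alone. Yes if TC Cream carries one too, which is not stated |

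The sentence that the products could not be distinguished asserts a result and gives no mechanism for it.

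**Step 2: who meets the labels?** Labels stay on the interior and exterior packages (3.5.2). Subjects apply the cream twice daily for 8 weeks (3.4.2) and bring back medication and packaging at each visit (3.4.3). The investigator or a designee keeps the inventory (3.5.1). Designated clinical staff handle receipt, dispensing and accounting (3.5.2).

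**Step 3: does another section supply a safeguard?** None describes coded label text, an unblinded dispenser or a blinded assessor kept apart from drug handling.

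**Step 4: how sensitive would a trial of this size be to biased scoring?** This is an illustration only. The documents give neither a vehicle response rate nor a bias size. The inputs are n = 44 per arm (9.1), two-sided 0.05 (9.2.4), an assumed vehicle success rate p of 10%, 20% or 30%, no true effect, and an assumed bias b that adds 5 or 10 percentage points to the TC arm. With p̄ = p + b/2 and the normal approximation for two proportions (close to the planned t-test on response rates):

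P(significant, favouring TC) = Φ[(b − 1.96·s0)/s1], where s0 = √(2p̄(1 − p̄)/44) and s1 = √([(p + b)(1 − p − b) + p(1 − p)]/44).

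Example, p = 10% and b = 5 points: s0 = √(2 × 0.125 × 0.875/44) = 0.0705; s1 = √((0.1275 + 0.09)/44) = 0.0703; (0.05 − 0.1382)/0.0703 = −1.25; Φ = 10.5%.

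| Assumed vehicle rate | No bias | b = 5 points | b = 10 points |
|---|---|---|---|
| 10% | 2.5% | 10.5% | 25.7% |
| 20% | 2.5% | 8.1% | 18.9% |
| 30% | 2.5% | 7.2% | 16.3% |

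Under these assumptions even a small bias would multiply the false-positive rate. The table does not estimate what the bias would be.

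**The case against.** The strongest reply has four parts.

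- **The expiry sentence is ambiguous.** It can mean that the control, too, carries an expiry date. A reader might infer that the date is certain to appear on the control only. That is the natural reading, but the documents never say that the TC Cream label lacks one.
- **Name and strength need not unblind.** The same list of items applies to each container. If the printed text is common to both arms it reveals nothing, and the stated intent is matching packaging. This stands, but the plan does not say the text is common.
- **Not everyone could read the arm off the tube.** A reader might infer that every subject would be unblinded at first dispensing. A subject holding a single kit could not interpret the presence of an expiry date without knowing the rule. Drug handling may also fall to staff other than the assessor. The documents neither separate these roles nor equate them, so complete unblinding is a worst case and not a finding.
- **No size can be given.** A reader might want to set an assumed shift in success rates against the difference that 44 per arm can detect. The documents give no bias size and no vehicle rate, so such a comparison would only restate its assumptions.

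These replies limit the claim. They do not remove the contradiction, because no section reconciles the label sentences with the claim of indistinguishability, and whoever prepares the labels would work from that text.

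**Conclusion.** Section 3.5.2 is wrong as written. It promises products that cannot be told apart and sets label rules that, followed literally, could tell them apart for anyone who handles the tubes and knows the rule. This conflicts with section 3.2 and puts the investigator-scored ISGA at risk of assessment bias.

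The conclusion rests on the wording alone. It does not show that the blind was broken, and no label specimen is available to check. The size of any bias is unknown; the false-positive rates of about 7% to 26% in the illustration hold only under its assumed vehicle rates and biases.

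The loose wording on analyst blinding in section 3.2 is a separate and secondary point. It does not bear on whether the tubes reveal the arm.

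**What to change.** Replace the label sentences in section 3.5.2 with text such as:

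> All tubes and kits in both arms carry the same label text: protocol number, kit number, 'TC Cream or vehicle', the same expiry or retest field, and storage conditions. No arm-specific name, strength or lot number appears. The key linking kit, lot and arm is held with the randomization list.

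Separately, change section 3.2 so that all data analysts remain blinded until database lock.

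The cost is label text, before packaging or as a relabel, and one sentence in section 3.2. Sample size, visits and endpoints are unaffected.

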3.5.3 Storage Conditions

Store at room temperature 15° C - 25° C (59° F - 77° F). Do not freeze. Keep tightly closed and away from light. Keep out of reach of children.

[figure not shown]
Protocol Version: 00

3.5.4 Stability

The study agent (both drug substance and finished product) is stable for at least 36 months at room temperature in shaded places

